### Test meal preparation and distribution

The test meals will be prepared at a centrally located building in the Mirpur slum. The building, which will be rented for 6 months, will be used to conduct the health examination of the children, blood drawing, food storage and cleaning, cooking and feeding of test meals to 180 children. Four head cooks, 24 local kitchen helpers and 7 research assistants will be in charge of preparing and distributing the meals.

The head cooks will be in charge of cooking all dishes, while the local kitchen helpers are needed, especially for the peeling, cleaning and cutting of the vegetables. On a daily basis, four dishes (rice, mola fish curry, rui fish curry and vegetable curry) will be prepared; approximately 130 kg boiled rice, 70 kg vegetable curry, 10 kg mola curry and 15 kg rui curry. In addition, the local kitchen helpers will help in bringing the children to the building, make the children feel welcome, prepare them for eating (for example seeing that they wash their hands), arrange them in intervention groups, and in preparation for receiving the different test meals. They will also assist with meal distribution, encourage and motivate the children to eat the test meal, especially all of the fish curry. In order to ensure that the children eat all the fish curry served, they will first be served the fish curry along with the rice and after finishing the fish curry, they will be served the vegetable curry. The test meals will be served at lunchtime (1300 - 1400 h).

The research assistants will be responsible for instructing and overview the kitchen helpers, supervising that the amounts and procedures described in the recipes are followed by the cooks, weigh the amounts of raw foods to be cooked in each dish, weigh the dishes and serve the test meals. Rice, vegetable curry and fish curry will be weighed and served separately to each child in disposable plastic containers. Disposable plastic containers will be used for hygienic purposes, ease of weighing separate portions as well as ease of administration. Drinking water will be given *ad libitum*. The containers will be marked with the child's identification number. Leftovers of each dish will be weighed to calculate total intake.

We shall have 3 floors of a building to accommodate 3 groups of children.

For the nutrient analyses of dishes, duplicate samples will be collected in labelled plastic boxes and stored frozen. One sample each of cooked rice (n=5) and vegetable curry (n=5) will be taken biweekly. For the three fish dishes, one sample each will be taken every week (n=9), in total 27. The duplicate samples will be used for chemical analyses of dry matter, vitamin A, energy, protein, fat, iron, calcium and zinc.

In order to motivate the children to comply with the study procedure, each child will be given a notebook, a pen and an identification card that can be hung around his/her neck. The identification card will be colour coded (each intervention group having a different colour) and include the child's name, ID number, parents' names, camp name, dates of study and the child's picture.

The research assistants will record all data collected daily with respect to attendance of the children, leftover dishes and duplicate samples and enter them in a computer programme.

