#### **Preliminary Observations**

International Centre for Diarrhoeal Disease Research, Bangladesh (ICDDR,B): Centre for Health and Population Research (ICDDR,B) and the principal investigator have been conducting different scientific research in the proposed study area, Mirpur slum in Bangladesh for the past 7 years. Mirpur slum is a suburb of Dhaka, which is 10 km from ICDDR,B. The short distance from Mirpur slum to ICDDR,B facilities makes it feasible to carry out field studies in the area. In addition, ICDDR,B has a local office in the Mirpur slum, which employ both ICDDR, B professionals and local community people. There are good infrastructure, records of the area and households as well as a good rapport and collaboration with the community leaders and inhabitants in the area. Based on previous ICDDR,B studies, the population in this area suffer from various micronutrient deficiencies such as vitamin A, iron and zinc deficiency.

A pilot study was conducted at the local office in the Mirpur slum in October 2000 to develop and test the recipes to be used in the study as well as the procedures and the logistics, in terms of physical set up and manpower of carrying out the study.

The test meals in the 3 different intervention groups have been designed and will consist of rice, a blended fish curry and a vegetable curry. The dishes developed were cooked and served to 20 children (4-11 yrs age) for 5 days. Cooked rice (200-450g on various days), and cooked vegetables 200g were offered and eaten by the children. Cooked and blended *mola, rui fish* (60 g on day 1-3 and 90 g rest days) were eaten by the children. Based on their feedback, adjustments were made with respect to ingredients in each recipe and amount of each dish to be served in the test meal. Based on the children's behaviour and reactions, it was observed that they needed motivation to eat the test meals, at least initially, but at the same time, they liked the dishes, expressing that they were very tasty.

Samples of raw mola and rui and the corresponding cooked fish curries were taken to determine the cooking loss of vitamin A. Samples of the cooked vegetable curries were also taken for determination of vitamin A but these have not yet been analysed. We assumed that the cooking loss of vitamin A could be maximum 50%.

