### Design and intervention groups

A house to house survey will be conducted in about 4 camps purposely selected in order to achieve proposed target children (inclusions criteria in points 1-4 on the next page and **Appendix 1: Household mapping form**).

For the intervention study only marginal vitamin A deficient children (based on serum retinol concentrations 0.35-0.70  $\mu\text{mol/L}$ ) will be selected, since only in these children is the intervention expected to have an increase in serum retinol concentration. Expecting that one out of three children (33%) has marginal vitamin A deficiency, approximately 550 children who meet the inclusion criteria listed in points 1-7 below, will be *screened* to determine their serum retinol concentration.

Children who meet all of the following inclusion criteria will be selected for *screening*:

1. Preschool children of both sexes between 3 and 7 years of age from families of lower socio-economic status
2. Children who eat fish
3. Taking no vitamin A supplementation and multivitamin in the preceding 6 months
4. Not suffering from serious illness like: persistent or chronic diarrhoea, tuberculosis, chronic pneumonia disease, asthma, diabetes type 1, hepatitis B, cardiac malformation, measles, respiratory tract infections, acute diarrhoea and skin infections
5. Parents and children who give their consent to participate in the study
6. Children who pass the clinical health examination (Appendix 2: Child clinical health examination form): For example having no clinical signs of vitamin A deficiency, chronic diseases, measles, respiratory tract infections, acute diarrhoea, skin infections and severe malnutrition
7. On the time of blood drawing, have no fever and show no clinical sign of acute infections, including diarrhoea

Children (n=180) identified as marginal vitamin A deficient (based on serum retinol concentrations 0.35-0.70  $\mu\text{mol/L}$ ), will be randomly allocated to either of the following three intervention groups and enrolled in the feeding trial at *baseline*. In each intervention group, there will be 60 children, receiving the same basic meal and either:

- 1) small fish, mola (vitamin A rich group) or
- 2) big fish, rui (negative control group, no/low vitamin A) or
- 3) rui and purified vitamin A, retinyl palmitate (positive control group)

All children will receive one meal per day, replacing one of the meals at home for 6 days a week for 9 weeks.

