### **Food intake**

One 24 h dietary recall of all 550 children will be conducted as baseline information in order to assess habitual food and nutrient intakes at the group level. In addition, a semi-quantitative dietary assessment of vitamin A intake will be done in order to assess the risk of inadequate dietary vitamin A intake at the group level.

During the feeding trial, between *baseline* and *endpoint*, intakes of nutrients (vitamin A as well as energy, carbohydrate, protein, fat, iron, zinc and calcium) from foods not provided in the test meals will be calculated from biweekly food consumption surveys of the 180 children, using the 24 h recall method.

The results will be used to calculate the total daily intakes of nutrients in each treatment group during the feeding trial based on the following:

1) data from the food consumption surveys conducted between *baseline* and *endpoint* (mean of 4-5 dietary recalls) and 2) the amount of food given in the dishes (corrected for leftovers) and from the chemical analyses of duplicate samples of the dishes (please see below).

The total daily intakes of nutrients during feeding trial will be compared between treatment groups as well as with habitual food and nutrient intake.

The conduction of the 24 h recall method will be based on the method described by Gibson, 1990. The questionnaire is enclosed as Appendix 5.

The method used for conducting the semi-quantitative dietary assessment of vitamin A intake will be based on the method proposed by the International Vitamin A Consultative Group (IVACG) (Underwood *et al*, 1989). The questionnaire is enclosed as Appendix 4.

The health assistants will be trained, the questionnaires will be pre-tested, the health assistants will be checked in the field by supervisors and the filled out questionnaires will be checked daily.

A random check of 5% of the total number will be conducted in order to test the reliability of the 24 h dietary recalls, semi-quantitative assessment of vitamin A intake and morbidity questionnaires. This means that another person repeats the visit in the same household on the same day for 5% of the households. A quick comparison of the field assistant's questionnaire and the supervisor's questionnaire is done on the same day. At *baseline*, the field system may be adjusted to correct the faults.

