#### Response:

- a) Habitual food and nutrient intake will be measured by one 24 h recall at screening (n=700) as stated in Experimental Design and Methodology in the application form. These results are adequate for assessing food and nutrient intake at group level.
- b) Habitual intake of vitamin A rich foods and vitamin A intake will be measured using a food frequency questionnaire on vitamin A rich foods at screening (n=700) as stated in Experimental Design and Methodology in the application form. The results will be used to assess habitual intake of vitamin A rich foods and vitamin A intake at individual level.
- c) We agree that weekly 24 h recall of food intake (except test meals) during the feeding trial is perhaps too frequent. We have reduced the number of 24 h recall from weekly to biweekly. The results will be used to assess the total daily intakes of nutrients in each treatment group (mean of five recalls). This will also be used to compare with habitual food and nutrient intakes.
- d) In Experimental Design and Methodology in the application form, it is stated that "duplicate sample of the dishes will be taken each day and pooled weekly samples of each dish will be used for chemical analyses of dry matter, vitamin A, energy, protein, fat, iron, calcium and zinc". We agree with the reviewer's comment that the burden of the nutrient analyses of dishes is great and therefore this has been revised. One sample each of cooked rice (n=5) and vegetable curry

(n=5) will be taken biweekly for nutrient analyses. For the three fish dishes, one sample each will be taken every other day in each week and pooled weekly (n=9) for nutrient analyses.

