### Thrasher Research Fund

[name]  
 [name]  
 [contact]  
 www.thrasherresearch.org

7 August 2001

[name]  
 Assoc. Scientist & Head  
 Nutritional Biochemistry Division  
 ICDDR,B: Ctr. for Health and Population Research  
 [name]  
 [name]  
 Bangladesh

Dear [name]:

This Award Letter is to advise you that the Thrasher Research Fund ("Fund") has approved your application for a grant (the "Grant") described below, to be made upon the following terms and conditions:

1. The Principal Investigator is [name]. The project name is "The effectiveness of vitamin A-rich small fish in improving vitamin A status in children (3-7 yrs.) in Bangladesh." The total project grant award for the period of 1 October 2001 to 30 September 2004 is \$203,287. The Supervising Institution is ICDDR,B: Centre for Health and Population Research.
2. This Grant is awarded on two conditions. The first condition is that the changes to the research protocol to which you have previously agreed be incorporated. These changes include those listed in your response to reviewers' comments (received 18 June 2001, copy attached), the use of children 3-7 years of age rather than 7-11 years of age, and performance of relative dose response tests on a subsample of each study group, both pre-and post-intervention. The second condition is that the attached revised budget dated 27 July 2001 supersedes any previous requests.
3. By acceptance of the Grant, the Principal Investigator and the Supervising Institution expressly acknowledge and accept all of the conditions in this Award Letter as well as the conditions stated in the document entitled Conditions of Grant, a copy of which is attached and made part of this contract by this reference. Please pay particular attention to the details stated in this Award Letter as well as in the Conditions of Grant, and retain them for future reference. Unauthorized reallocation of funds or failure to submit semiannual reports as required will give the Fund the right, but not the obligation, to suspend the Grant. If suspended, the Grant can only be reinstated upon written authorization from the Fund. Unless otherwise specifically stated in this Award Letter, this Grant shall be paid to the Supervising Institution under whose supervision the Principal Investigator shall be responsible for the research and other activities required to complete the project.

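### Read literally, the protocol measures fish-dish vitamin A on 9 of 54 cooking days; the weekly pooling promised to the funder would cover 27 days with the same nine assays per dish

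*Protocol*

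**What the plan says.** The sampling rule stands in the protocol under Test meal preparation and distribution and is repeated under Nutrient analysis of dishes: "For the three fish dishes, one sample each will be taken every week (n=9), in total 27". Neither place mentions pooling.

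Appendix 12, in the reply to the funder's first reviewer (item 1.2.1 d), sets a different rule: "For the three fish dishes, one sample each will be taken every other day in each week and pooled weekly (n=9) for nutrient analyses". Item 2 of the award letter makes the grant conditional on incorporating agreed protocol changes and adds: "These changes include those listed in your response to reviewers' comments".

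The surrounding facts are these.

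- Children receive one test meal, "replacing one of the meals at home for 6 days a week for 9 weeks" (Design and intervention groups).
- The curries are made fresh: "On a daily basis, four dishes (rice, mola fish curry, rui fish curry and vegetable curry) will be prepared".
- Intake from the test meals is computed from "the amount of food given in the dishes (corrected for leftovers) and from the chemical analyses of duplicate samples of the dishes" (Food intake). Nutrient intake during the study is then a covariate in the analysis of covariance (Data Analysis).
- The nominal content of the mola portion depends on an assumption: "We assumed that the cooking loss of vitamin A could be maximum 50" per cent (Preliminary Observations).

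**The concern.** The dish assays are the only planned measurement, during feeding, of how much vitamin A a gram of each fish dish contains. Blending makes one day's mola curry uniform, but it does nothing about differences between days. The mola is caught over four to six months, frozen in daily portions and cooked in a new batch each day, so content may differ from day to day.

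An error in the measured content is shared by every child who eats that dish. It therefore does not average out over the 60 children in a group. It carries into the reported vitamin A intake of the mola group, into the intake covariate, and into the reading of a weak mola response: poor use of the vitamin, or less of it on the plate than planned.

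The body of the protocol appears to have given up two thirds of the sampled days without saving an assay. The rice and vegetable rule (five samples each, every two weeks) is the same in the reply and in the protocol. For the fish dishes the every-other-day and pooling terms have gone, and no reason is given.

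**Working it through.** **The plan's own count.** 3 fish dishes × 9 weeks × 1 sample = 27, as stated.

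**Days covered, per dish.**

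- Feeding days: 9 weeks × 6 days = 54.
- Protocol, read literally: 9 × 1 = 9 days, and 9/54 = 16.7%.
- Reply to the funder: every other day is 3 of 6 days, so 9 × 3 = 27 days, and 27/54 = 50%.
- Assays: 9 per dish under either rule, 27 over the three dishes. (That 27 counts assays over three dishes; the 27 days are for one dish.)

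**Day-to-day part of the standard error.** Without a finite-population correction the error of the mean content is CV/√n. The ratio of the two schemes is √(9/27) = 0.58, a cut of about 42% whatever the CV.

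Because there are only 54 days, a correction is reasonable: CV × √((1 − f)/n), with f = 1/6, n = 9 or f = 1/2, n = 27. This treats the days as a random choice within each week. The multipliers are √(0.8333/9) = 0.304 and √(0.5/27) = 0.136, a ratio of 0.45, or a cut of about 55%.

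The documents give no day-to-day CV, so the absolute figures rest on an assumed range (with the correction, no assay error):

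| Assumed day-to-day CV | 9 days | 27 days, pooled |
|---|---|---|
| 10% | 3.0% | 1.4% |
| 20% | 6.1% | 2.7% |
| 30% | 9.1% | 4.1% |
| 40% | 12.2% | 5.4% |

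**Adding assay error.** With nine assays either way, assay variance contributes (assay CV)²/9 to both schemes. For an assumed assay CV of 10%:

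- Day-to-day CV 20%: √(0.20² × 0.8333/9 + 0.10²/9) = 6.9%, against √(0.20² × 0.5/27 + 0.10²/9) = 4.3%.
- Day-to-day CV 10%: 4.5% against 3.6% by the same formulas.

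The gain shrinks as assay error grows relative to day-to-day variation.

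**Why the nominal figure is no substitute for mola.** Raw mola is given as 2,400–3,000 RE per 100 g. For 45 g at a 50% loss this is 45 × 24 × 0.5 = 540 RE to 45 × 30 × 0.5 = 675 RE, against a nominal figure of about 500 RE. The loss itself is an assumed maximum.

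**The case against.** Several points on the other side stand.

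- **Wording.** One sample a week with nine per dish is also what nine weekly pools would yield, so the protocol may be using shorthand. This cannot be excluded. Field staff following the text literally would still take one portion on one day.
- **Status of the reply.** A reader might infer that the protocol breaches a grant condition. The documents do not support going that far. The protocol departs from the same reply elsewhere: 700 screened children became 550, a modified dose-response test at screening gave way to the relative dose response test in subsamples, and the later stool tests were dropped. The award letter itself required the relative dose response test that the reply had ruled out. The letter supports reconciling the texts, not reading the reply as binding line by line.
- **Delivered dose.** A reader might infer that the dose is unknown on the other 45 days. It is not: each child's dishes and leftovers are weighed, so only content per gram rests on the weekly samples. Nor does the plan fall back on the nominal 500 RE, since Food intake already uses the assays.
- **Which dish.** Rui has little or no vitamin A, and retinyl palmitate is added to each child's meal at serving, not in the pot. Batch variation is therefore chiefly a mola matter.
- **Bias.** Sampling on a fixed weekday could miss a weekly pattern, but nothing in the protocol says the weekday is fixed or that such a pattern exists.
- **Size.** A fixed recipe, blending and frozen daily portions may hold the variation below 20%. A larger obstacle to comparing mola with retinyl palmitate is that about 80% of mola's vitamin A is dehydroretinol (Appendix 12), which more sampling days do not address.
- **Proportion.** A funder's reviewer thought the composition work excessive, and the sampling was cut in response. Nine assays per dish is defensible; the point here is which days feed them.

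**Conclusion.** The point holds as a minor one. On a literal reading the protocol samples each fish dish on 9 of 54 cooking days, where the investigators' reply had 27 of 54 for the same nine assays. The weekly scheme is valid but less precise. Pooling would cut the day-to-day part of the standard error by about 42%, or about 55% with the finite-population correction. In absolute terms, for assumed day-to-day CVs of 10–40%, the error of the mean content would fall from 3.0–12.2% to 1.4–5.4% before assay error, which pooling leaves as it is.

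The benefit lies in describing the vitamin A content of the mola curry, in the intake covariate, and in interpreting mola against the positive control. It would be tempting to conclude that the efficacy result is compromised. It is not: the randomised comparison of change in serum retinol does not depend on these assays.

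**What to change.** Reconcile Test meal preparation and distribution and Nutrient analysis of dishes with Appendix 12. State that a duplicate portion of the mola curry is taken every other feeding day, that portions are pooled within each week, and that the nine weekly pools are assayed. For consistency apply the same rule to the other two fish dishes, and say that the positive-control portion is taken after the retinyl palmitate has been added. If a weekly pool was always meant, adding that wording to both sections is enough.

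The cost is two extra frozen portions per dish per week, freezer space and a pooling step. The number of assays stays at 27. The one loss is that variation between days within a week can no longer be seen.

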### **Biochemical indicators of vitamin A and iron status**

The following biochemical indicators for assessing vitamin A and iron status will be measured at *screening* (550 children) and at *endpoint* (180 children) from 4 ml blood drawn by venepuncture in the morning: retinol, retinol binding protein, prealbumin, haemoglobin, ferritin, transferrin receptor. Changes in vitamin A and iron status will be calculated by subtracting the values at *screening* from those at *endpoint*.

In addition, as an indirect measure of liver vitamin A stores the RDR test will be performed on two different subsamples of children (15 children per intervention group, in total 45 children) at *baseline* and at *endpoint*. The RDR method is included in order to confirm low vitamin A status at *screening* and improvement by the intervention in terms of body stores, since serum retinol levels can be artificially lowered by concurrent infection.

RDR will be conducted by administering 3.5  $\mu\text{mol}$  (1000 $\mu\text{g}$ ) retinol equivalent as retinyl palmitate orally. Venous blood will be obtained at 0 h (4 ml blood) and 5 h (1 ml blood) after administering the retinyl palmitate dose. The RDR value will be calculated as  $[(\text{retinol } 5\text{h} - \text{retinol } 0\text{h}) / \text{retinol } 5\text{h}] * 100$ . Values  $\geq 20\%$  are considered abnormal (Flores *et al*, 1984). The 0 h blood sample will also be used for the analysis of vitamin A and iron status indicators as described above.

Indicators of iron metabolism are included due to the interdependence between vitamin A and iron (Wolde-Gebriel *et al*, 1993; Suharno *et al* 1992; Bloem *et al* 1989; Mejia *et al* 1977). The ratio between ferritin and transferrin receptor will be used as an indicator of iron status as suggested at the INACG (International Anaemia Consultative Group) meeting held in Hanoi in February 2001.

